10.4 Week 8/End of Study or Early Termination (Visit 4)

The following activities will take place at Visit 4A (first day of 2-day visit):

- Obtain body weight;
- Obtain vital signs (blood pressure, heart rate, respiration rate and temperature);
- Collect PK blood sample for assessment of phentermine and topiramate levels (prior to dosing);
- Record any adverse events reported or observed;

- Record any changes in concomitant medications;
- Perform a urine pregnancy test (WOCBP only) and remind subject about contraception;
- Set up 24-hr ABPM monitoring equipment;
- Collect study drug from previous visit, assess treatment compliance, and perform drug accountability;
- Administer last daily dose of study drug, record time of dosing, then initiate ABPM monitoring; and
- Provide subject with instructions for proper handling of ABPM device and remind the subject to return to the clinic in 24 hours to complete study.

The following activities will take place at Visit 4B (second day of 2-day visit):

- Record any adverse events reported or observed (note that as described in [Section 12.3](#) adverse events known to the investigator and occurring within 28 days after the last dose of study drug must be reported);
- Record any changes in concomitant medications;
- Perform a physical examination;
- End 24-hr ABPM monitoring, disconnect devices, and upload data upon verifying successful ABPM; if verification of successful ABPM cannot be made, repeat 24-hr ABPM setup as described for Visit 4A and bring subject back in 24 hours to complete evaluation;
- Perform 12-lead electrocardiogram (ECG);
- Obtain full blood chemistry, hematology, and urinalysis for laboratory testing;
- Obtain vital signs (blood pressure, heart rate, respiration rate and temperature); and
- Discontinue subject's study participation.

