 - ≥ 80 bpm at baseline and ≥ 10 bpm increase from baseline; ≥ 90 bpm at baseline and ≥ 10 bpm increase from baseline; ≥ 100 bpm at baseline and ≥ 10 bpm increase from baseline;
- Mean percent change in body weight from baseline to Week 8.

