5.4 Per Protocol (PP) Population

PP Population will be comprised of ITT subjects who met all of the following criteria:

- Compliant to study treatment (defined as $\geq 80\%$ treatment compliance as specified in [Section 6.5](#));
- Last daily dose of study drug administered on the same date that ABPM was initiated at Visit 4A (first day of Week 8/End of Study or Early Termination);
- Had at least 23.5 hours of ABPM data (i.e. blood pressure and heart rate data) at baseline and at Week 8/End of Study or Early Termination, and at least 75% of 24-hr ABPM readings (or equivalently 48 readings during the 24-hr period) are not missing;
- Subjects with any major protocol deviation that had impact on ABPM readings will be excluded from the PP Population.

The PP population will be used to assess the primary and secondary endpoints as primary analyses. Subject inclusion in the PP population will be determined and documented prior to database lock and treatment unblinding.

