7.2.2 Analyses of Secondary Endpoints

Secondary endpoints including change from baseline to Week 8 in mean DBP as measured by 24-hr ABPM, mean change in SBP and DBP from baseline to Week 8 as measured in clinic will be analyzed for the PP population using a similar ANCOVA model structure as that of the primary analysis. The model will comprise of treatment, stratification factors (sex, age and hypertensive status) and baseline value of the dependent variable as a covariate. Adjusted means (LS Mean \pm standard error) with associated two-sided 95% confidence intervals for the between-treatment comparisons and for the changes from baseline will be reported.

The estimand, estimator, and estimate of these secondary endpoints are defined as follows:

Estimand	Population	Per Protocol
Endpoint		Changes from Baseline in Variable X at Week 8

	How to account for intercurrent events	The treatment policy strategy will be followed, whereby the observed value (if not missing) for the endpoint of interest will be used for analysis.
	Population-level summary	The between-treatment difference in changes from baseline to Week 8 in Variable X.
Estimator	Analysis	ANCOVA with treatment, stratification factors (sex, age and hypertensive status) and baseline value of variable X as a covariate.
Estimates	Primary to support the estimand	Between-group comparison (effect in VI-0521 minus effect in placebo [or phentermine]): 
 ✓ LSM for the between-group difference ✓ 95% CI of the LSM ✓ p-value
Estimates	Tributary	Within-treatment group comparison (effect at Week 8 minus the value at baseline): 
 ✓ LSM for the within-group difference ✓ 95% CI of the LSM ✓ p-value

Similar imputation method as described in [Section 7.2.1](#) will be carried out for missing DBP values from the 24-hr ABPM. For missing clinic SBP and DBP, data will not be imputed after mapping unscheduled visits.

Additionally, supportive analysis of the 24-hr mean DBP endpoint will be carried out similarly as described in [Section 7.2.1.2](#). Supportive analysis of the clinical SBP and DBP endpoint will be performed using the observed case data for the ITT population. Extra sensitivity analyses similar to the primary endpoint may be conducted on the secondary endpoints if applicable.

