7.2.3 Analysis of Exploratory Endpoints

Analysis of exploratory endpoints will be performed on the PP population using the observed case data.

All change from baseline exploratory endpoints will be analyzed using ANCOVA models in a similar manner to the primary and secondary endpoints. For the endpoints on percentage of subjects with a normal SBP and DBP ‘dipping pattern’ at Week 8, a Cochran-Mantel-Haenszel (CMH) χ^2 test that is stratified by sex, age and hypertensive status will be used for analysis. Corresponding estimates of the common Mantel-Haenszel relative risk will be provided along with 95% confidence intervals (CIs). For the endpoints on percentage of subjects meeting the BP or heart rate thresholds, descriptive summary will be provided.

Example SAS codes for CMH test are:

No sensitivity analysis is planned for the exploratory endpoints.

In addition, all 24-hr ABPM measurements including blood pressure and heart rate that are summarized in the endpoints will be presented in a listing.

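### Clinic BP, clinic heart-rate thresholds and body weight are analysed in a per-protocol set defined mainly by ABPM quality, so valid readings leave the main analysis because of inadequate ABPM

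*SAP*

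**What the plan says.** SAP 5.4 defines one PP set: "The PP population will be used to assess the primary and secondary endpoints as primary analyses". SAP 7.1 extends it to all efficacy analyses, with ITT in support where suitable. A member must meet four criteria:

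1. at least 80% capsule compliance;
2. last daily dose taken on the date the Visit 4A ABPM began;
3. adequate recordings, worded as "Had at least 23.5 hours of ABPM data (i.e. blood pressure and heart rate data) at baseline and at Week 8/End of Study" (an early-termination recording counts too), with at least 75% of readings (48) present;
4. no major deviation that affected ABPM readings.

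For the secondary endpoints, SAP 7.2.2 states that "mean change in SBP and DBP from baseline to Week 8 as measured in clinic will be analyzed for the PP population". It adds: "Supportive analysis of the clinical SBP and DBP endpoint will be performed using the observed case data for the ITT population". SAP 7.3.3 summarises clinic vital signs descriptively in the Safety population.

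For the exploratory endpoints, SAP 7.2.3 states: "Analysis of exploratory endpoints will be performed on the PP population using the observed case data". These include "Mean percent change in body weight from baseline to Week 8" and the percentages of subjects crossing clinic BP and heart-rate thresholds (SAP 4.3). The same section says: "No sensitivity analysis is planned for the exploratory endpoints".

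The Protocol places all analyses on ITT (13.1), and applies the primary endpoint's methods to the secondary endpoints (13.1.3) and the continuous exploratory endpoints (13.1.5).

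**The concern.** A per-protocol set is meant to hold subjects whose data on a given endpoint are a fair test of the treatment. Here the set was built for the ABPM endpoints and then applied to measurements made with a clinic cuff and a scale. The mismatch runs both ways. It is too narrow, because a subject whose Week 8 recording falls short loses valid clinic BP and weight from the main analysis. It is also too loose, because criterion 4 does not remove a subject whose only major deviation affected the clinic reading.

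The clinic thresholds are tabulated at each post-baseline visit, so a sound Week 4 reading also goes when the Week 8 recording is inadequate.

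At stake are precision and comparability. Clinic SBP and DBP are in the formal testing hierarchy. The exclusions arise mostly at Week 8, after randomisation, and for a reason that says nothing about the quality of the clinic measurement. This would be a defect even if PP were accepted as the primary population.

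**Working it through.** **Criteria against endpoints**

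| SAP 5.4 criterion | Bearing on clinic BP and weight |
|---|---|
| ≥80% compliance | Relevant |
| Dose on ABPM start date | Weight: none as a dose effect, since weight is taken only at 4A and listed before the dose. Clinic BP: depends on which Week 8 reading is used |
| ≥23.5 h and ≥75% of readings, both visits | None |
| Major deviation affecting ABPM | Wrong instrument |

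The reading count is consistent: 16 h × 3 + 8 h × 2 = 64 scheduled readings, and 0.75 × 64 = 48, so 16 may be missing.

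**Which Week 8 clinic BP?** In Protocol 10.4, vital signs come early in the 4A list, and a later item reads "Administer last daily dose of study drug, record time of dosing, then initiate ABPM monitoring". Vital signs are taken again at 4B, the day after that dose. SAP Table 7-1 labels both 4A and 4B as Week 8. SAP 7.1.5 takes the later of multiple assessments at one visit, which could select 4B. The three-reading footnote in Protocol Appendix 1 is attached to 4A but not to 4B. The documents do not settle the choice.

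**Coverage outside PP**

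| Endpoint | Main set | Other named analysis |
|---|---|---|
| Clinic SBP/DBP change | PP | ITT observed case (supportive); Safety, descriptive |
| Clinic BP and heart-rate thresholds | PP, descriptive | None |
| Body weight | PP, observed case | None |

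**The plan's sample size.** Inputs from SAP 8: SD 10, difference 3 mmHg, two-sided alpha 0.05, power 80%, dropout 5%.

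- n = 2 × (1.960 + 0.842)² × 10² / 3² = 174.5, rounded up to 175 per arm.
- 175 / 0.95 = 184.2, rounded up to 185. The stated figure is reproduced. The exact t-test needs 176 per arm.
- Evaluable after dropout: 185 × 0.95 = 175.75, about 176. Nothing is allowed for PP exclusions.

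**Illustration of the loss.** The documents give no ABPM failure rate and no SD for clinic BP or weight. I assume 5–20% excluded from 176 per arm and borrow the ABPM planning values. SE = 10 × √(2/n); noncentrality = 3 / SE; power comes from the noncentral t with 2n − 2 df; relative CI width = √(176/n).

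| Excluded | n per arm | SE | Noncentrality | Power | CI width |
|---|---|---|---|---|---|
| 0% | 176 | 1.066 | 2.814 | 80.1% | 1.000 |
| 5% | 167 | 1.094 | 2.741 | 78.0% | 1.027 |
| 10% | 158 | 1.125 | 2.666 | 75.8% | 1.055 |
| 15% | 150 | 1.155 | 2.598 | 73.6% | 1.083 |
| 20% | 141 | 1.191 | 2.519 | 70.9% | 1.117 |

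**The case against.** **The loss may be small.** This stands. Randomisation follows a verified baseline recording (Protocol 10.2), and the site checks in Protocol 11.4 (80% valid, 24 hours, no gap over two hours) are stricter than the PP thresholds. Failed recordings, including those at Week 8, are to be repeated. In the 5% case the illustrative cost is about two points of power.

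**The power figures belong to another endpoint.** This also stands. SD 10 and 3 mmHg are planning values for 24-hour SBP. The plan claims no power for clinic BP, which is tested last, after every ABPM SBP and DBP step has succeeded (SAP 7.1.2.1). A reader might infer that the trial loses up to nine points of power on clinic BP. The documents support no such statement.

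**The dose-date rule does useful work.** It serves as an on-treatment check. Without it, 80% compliance over about 56 planned doses allows 0.20 × 56 = 11.2, so up to 11 missed capsules, possibly the last ones. The rule should be replaced for these endpoints, not just deleted.

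**Inclusion does not clearly hinge on a later dose.** A reader might infer that a clinic BP reading is kept or dropped according to a dose taken after it. That would hold if the 4A reading is used. If 4B is used, the dose comes first. The inference is safe only for weight.

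**Restoring ITT would cure this.** It would. What remains is that, if PP is kept, its criteria do not suit these endpoints.

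**Conclusion.** The point holds as a cheap improvement. One ABPM-based PP set is the main population for clinic SBP/DBP and the only one named for body weight and the clinic threshold percentages. Subjects with valid clinic data but inadequate ABPM are therefore left out of the main analysis of endpoints that the device did not measure. The case is strongest for weight, which has an inferential analysis in PP and none named elsewhere. It is weaker for clinic BP, and weaker again for the thresholds, which are only descriptive.

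Three stronger readings are not supported:

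- A reader might infer that PP demands complete recordings. It allows a quarter of the readings to be missing.
- A reader might infer that clinic BP from excluded subjects is discarded. It returns in the supportive ITT analysis and the Safety summaries.
- A reader might infer that the results will be biased. The exclusions are mostly post-randomisation, so selection is possible, but nothing in the documents shows that ABPM failure differs by arm.

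The range of 78–71% power and 3–12% wider intervals rests on an assumed exclusion rate and borrowed ABPM planning values. It shows scale only.

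**What to change.** For clinic SBP/DBP, the clinic BP and heart-rate thresholds and body weight, do one of the following before PP membership is fixed, which SAP 5.4 places ahead of database lock and unblinding:

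- **Use ITT**, as the Protocol states. This also removes the Protocol–SAP conflict for these endpoints.
- **Define a clinic PP set in SAP 5.4** that keeps ≥80% compliance, removes the ABPM-completeness criterion, replaces the deviation criterion with major deviations affecting the clinic measurement, and replaces the ABPM-day dose criterion with an on-treatment criterion tied to the clinic reading used. Refer to this set in SAP 7.2.2 and 7.2.3.

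In either case, state in SAP 7.1.5 whether the 4A or the 4B vital signs supply the Week 8 clinic value.

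The cost is a few lines of SAP text and, for the second option, one extra population flag. The downside is that ABPM and clinic results would come from slightly different sets of subjects, which a table footnote can state.

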6 STUDY SUBJECTS

6.1 Subject Disposition

Counts and percentages of subjects who were screened, enrolled, randomized, randomized and not treated, completed or were discontinued from the study, as well as the reason for discontinuation, will be summarized by treatment group.

6.2 Demographic and Baseline Characteristics

Demographic and baseline characteristic data, including but not limited to, age, sex, race, ethnicity, hypertensive status, SBP, DBP, diabetic status (Yes/No for T2DM), height, weight, and body mass index (BMI) will be summarized by treatment group for subjects in the ITT population.

If a subject meets one of the following criteria, the subject will be counted as “Yes” for T2DM:

- Has a medical history of T2DM
- Uses concomitant antidiabetic medications (see [Section 6.6](#) for concomitant medications)
- Has baseline lab fasting glucose ≥ 126 mg/dL (see [Section 7.1.3](#) for the definition of baseline)

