8.1 Inclusion Criteria

To be eligible for enrollment into this study, subjects must meet all of the following criteria at Screening (unless otherwise specified):

1. Overweight or obese adult males and females 18-75 years of age with a BMI $\geq 27 \text{ kg/m}^2$;
2. Medical diagnosis of at least 1 weight-related comorbidity (i.e., hypertension, dyslipidemia, type 2 diabetes mellitus or prediabetes, or obstructive sleep apnea);
3. Must be ambulatory, willing, and able to wear ABPM monitor apparatus for 24 hours during two study measuring visits, at Baseline and Week 8/end of study or early termination;
4. Screening laboratory values that are within the ranges specified below:

a. Bicarbonate	$\geq \text{LLN}$
b. AST and ALT	$< 3 \times \text{ULN}$
c. HbA1c	$\leq 7.5\%$
d. TSH	$\leq 1.5 \times \text{ULN}$
e. Triglyceride	$\leq 400 \text{ mg/dL}$
f. Creatinine clearance	$\geq 60 \text{ mL/minute (MDRD)}$
5. Females of childbearing potential must be using adequate contraception, defined as double barrier methods, stable hormonal contraception plus single barrier method, or previously documented bilateral tubal ligation. Women are considered of childbearing potential unless they are ≥ 50 years of age with spontaneous amenorrhea for at least 12 months or have had a hysterectomy and/or bilateral oophorectomy;
6. Provide written informed consent; and
7. Willing and able to comply with scheduled study visits, treatment plan, laboratory tests, and other study procedures.

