6.6 Concomitant Medications

The latest World Health Organization Drug Dictionary (WHO-DD) will be used to categorize verbatim descriptions of non-study medications into the Anatomic Therapeutic Chemistry (ATC) classification system. Each verbatim name will be classified by anatomical main group (ATC level 1), therapeutic subgroup (ATC level 2), pharmacological subgroup (ATC level 3), chemical subgroup (ATC level 4), preferred term, and trade name (if appropriate).

Concomitant medications are referred to non-study medications that have been used on or after receiving the first randomized study medication. Medications will be categorized into 3 types:

Pre-treatment medications: any non-study medications that started and stopped prior to receiving the first randomized study dose.

Prior concomitant medications: any non-study medications taken before the first randomized study dose date and continued beyond the first randomized study dose date.

New concomitant medications: any new non-study medications that started on or after receiving the first randomized study medication.

Counts and percentages of subjects receiving concomitant medications, prior concomitant medications, and new concomitant medications will be summarized by treatment group and ATC classification level 4 and preferred term for the ITT population. Additionally, concomitant medications used for management of blood pressure or diabetes, if any, will be summarized separately.

Pre-treatment medications will be provided in a listing.

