7.2.1.3 Subgroup Analyses of Primary Endpoint

The primary efficacy analysis will be performed for the following subgroups for the PP population:

- Sex (male and female);
- Age (< 50 and \geq 50 years);
- Race (white and not white);
- Hypertensive status (no medical diagnosis of or treatment for hypertension; medical diagnosis of hypertension treated with 0-2 antihypertensive agents; or medical diagnosis of hypertension treated with 3 or more antihypertensive agents).

The primary efficacy analysis for the subgroup medical diagnosis (T2DM and obstructive sleep apnea) may be performed if applicable.

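### The baseline type 2 diabetes flag in SAP 6.2 can be set by an antidiabetic drug started after the first dose, and can count prediabetes as T2DM

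*SAP*

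**What the plan says.** SAP 6.2 lists diabetic status among the demographic and baseline variables for the ITT population. The rule opens "If a subject meets one of the following criteria, the subject will be counted as" a yes, so one criterion is enough. The three criteria are:

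1. "Has a medical history of T2DM".
2. "Uses concomitant antidiabetic medications (see", with SAP 6.6 given as the source of the definition.
3. "Has baseline lab fasting glucose" of at least 126 mg/dL, with SAP 7.1.3 given for the meaning of baseline.

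SAP 6.6 states: "Concomitant medications are referred to non-study medications that have been used on or after receiving the first randomized study medication". It then separates prior concomitant drugs (taken before the first dose and continued past it) from new ones: "New concomitant medications: any new non-study medications that started on or after receiving the first randomized study medication".

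Protocol 8.1, inclusion 2, accepts any one weight-related comorbidity from this list: "hypertension, dyslipidemia, type 2 diabetes mellitus or prediabetes, or obstructive sleep apnea". Protocol 8.2, exclusion 10, allows antidiabetic medication that has been stable for three months and does not require a T2DM diagnosis. The SAP never mentions prediabetes.

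SAP 7.2.1.3 adds: "The primary efficacy analysis for the subgroup medical diagnosis (T2DM and obstructive sleep apnea) may be performed if applicable".

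**The concern.** A baseline characteristic should be fixed by information available before the first dose. Criterion 2 imports a definition that reaches past that point. A subject with no T2DM history and an unremarkable baseline glucose who starts an antidiabetic drug during treatment would be reported as diabetic at baseline. The need for T2DM rescue therapy is also a safety outcome compared between arms (SAP 4.4 and 7.3.6), so one event could count both as an outcome and as a baseline trait.

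The second weakness is separate. Criterion 2 asks only whether an antidiabetic drug is used, not what it is for. The protocol admits subjects on the strength of prediabetes and permits stable antidiabetic drugs, so the rule can relabel such a subject as T2DM.

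At stake is the accuracy of the baseline table. If the same flag also defined the T2DM subgroup, membership of that subgroup could depend on events after randomisation.

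**Working it through.** **Criteria side by side**

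- Criterion 1 (history) is pre-dose by nature.
- Criterion 3 (glucose) is tied explicitly to the baseline definition in SAP 7.1.3.
- Criterion 2 (drug use) is tied to SAP 6.6 instead. There, concomitant means prior concomitant plus new concomitant, and SAP 6.2 does not restrict itself to the prior type. The narrower category exists but is not used.

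**When a post-dose start changes the flag.** Three things must all hold: no T2DM history, baseline glucose below 126 mg/dL, and an antidiabetic drug begun on or after the first dose. Protocol 6.0 asks that concomitant medication stay fixed, with an exception only for blood-pressure rescue. Protocol 9.6.3 discontinues subjects who need any of four named antidiabetic classes. Other classes are not named there, so the route is narrow but open. Discontinued subjects who took a dose stay in the ITT baseline table. They can also reach the per-protocol population, because SAP 5.4 accepts early-termination recordings and SAP 6.5 counts compliance only over the time enrolled.

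**When prediabetes becomes T2DM.** A subject whose history records prediabetes but not T2DM, with glucose below 126 mg/dL and a stable antidiabetic drug, satisfies criterion 2 and nothing else. The result is a yes.

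**Partial dates.** Under SAP Table 7-2, a medication start date with day and month missing, in the same year as the first dose, is imputed to the first-dose date. SAP 6.6 then makes that drug new. An established drug recorded by year only would be lost if criterion 2 were simply limited to prior concomitant drugs, so the correction has to cover this case.

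**Size.** The documents give neither the prevalence of T2DM nor the use of antidiabetic drugs outside it, so the following is illustration only. Let *p* be the true T2DM prevalence (assumed 10–30%) and *q* the share of subjects without T2DM flagged solely through a drug, by either route (assumed 0.5–5%). With 185 per arm:

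- false yes = 185 × (1 − *p*) × *q*
- share of the yes group = false yes ÷ (185*p* + false yes)

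| *p* | *q* | True T2DM | False yes | Share of yes group |
|---|---|---|---|---|
| 30% | 0.5% | 55.5 | 0.6 | 1.2% |
| 20% | 1% | 37.0 | 1.5 | 3.8% |
| 10% | 5% | 18.5 | 8.3 | 31% |

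The range runs from trivial to material and depends entirely on the assumed inputs.

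**Design figures.** The stated 185 per group does not involve this flag. The normal approximation gives 2 × (1.96 + 0.8416)² × 10² ÷ 3² = 174.4, so 175, and 175 ÷ 0.95 = 184.2, so 185, as stated. Nothing in this point changes it.

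**The case against.** The strongest reply is that criterion 2 sits under a baseline heading and is written in the present tense, so pre-dose use is its natural reading. A programmer may well implement it that way. But the SAP sends the reader to a definition that says otherwise, and a derivation should not rest on ignoring its own cross-reference.

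It is also fair to say that post-dose starts should be rare in an eight-week study with medication held fixed. That stands, and it limits the size of the problem.

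Other planned summaries help. Medical history is tabulated by coded term (SAP 6.3), so recorded prediabetes will appear there, and prior and new drugs are summarised separately (SAP 6.6). These tables let a reader suspect misclassification, but they do not correct the flag.

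Three stronger readings are tempting, and the documents do not support them:

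- A reader might infer that the T2DM group is contaminated. The documents show only that it can be. Nowhere do they say that any subject with prediabetes takes an antidiabetic drug.
- A reader might infer that the randomised comparison within the T2DM subgroup is broken. SAP 7.2.1.3 makes that analysis optional, names it by medical diagnosis and does not refer to the SAP 6.2 rule. The flag's only stated use is descriptive.
- A reader might take the absence of screening HbA1c from the rule as an error. Inclusion 4c is an eligibility ceiling, not a diagnostic rule, and nothing in the documents shows that leaving HbA1c out misclassifies anyone.

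**Conclusion.** The point holds in a limited form. As written, SAP 6.2 and 6.6 together allow a baseline characteristic to be determined after randomisation, and allow prediabetes treated with a stable drug to be counted as T2DM. This is a stated rule that can give a wrong label, not merely a missing detail.

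The consequence is modest. T2DM status is not a stratification factor, a model term or part of the testing hierarchy, so the primary and secondary analyses do not depend on it. The exposure is the baseline table and, only if it draws on this flag, the optional subgroup analysis of the primary endpoint. The number of subjects affected cannot be derived from the documents, and no single percentage should be attached to it.

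**What to change.** 1. In SAP 6.2, limit criterion 2 to antidiabetic drugs in the prior concomitant category of SAP 6.6, and exclude new concomitant medications explicitly.
2. State how a drug is treated when Table 7-2 imputes its start to the first-dose date, so that established treatment with a year-only start date is not dropped by default.
3. Do not count as T2DM a subject whose medical history records prediabetes without T2DM and who qualifies only through an antidiabetic drug. Show prediabetes as its own category. A subject on an ongoing pre-dose antidiabetic drug with neither condition recorded would still count as T2DM, which keeps the criterion's apparent purpose of catching treated diabetes missing from the history.
4. State in SAP 7.2.1.3, before unblinding, that the T2DM subgroup uses this corrected pre-dose definition.

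A recorded T2DM indication for the drug should be required only if the CRF captures it. Protocol 9.6.4 says that medications are listed on the CRF but does not mention indication.

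The cost is a few lines of SAP text and one revised derivation from medical history, medication dates and baseline glucose. No visit or procedure is added. Settling it before unblinding matters because a later redefinition of the subgroup could look data-driven.
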